6.2.2 Prohibited Concomitant Medications during the Study

Administration of other commercial IVIG products during study is not allowed.

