## 2.2 Endpoints

### 2.2.1 Primary Efficacy Endpoint

The primary efficacy endpoint is all-cause mortality rate through Day 29.

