## 3.2 Treatment

### 3.2.1 Randomization Scheme and Treatment Arm Assignment

Subjects will be randomized 1:1 to receive either combination treatment with Gamunex-C plus SMT or SMT alone. A central randomization will be used for this study. A randomization list containing the randomization numbers and the corresponding randomized treatment assignments will be generated and be stored in a secured area that is only accessible to the randomization team.

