## 4. GENERAL CONSIDERATIONS FOR DATA ANALYSIS

Unless otherwise specified, continuous variables will be summarized using descriptive statistics (n, mean, standard deviation, median, minimum, and maximum). Categorical variables will be summarized showing the number and percentage of subjects within each category.

Summary results will be provided for each treatment group. All tabulations will be based on pooled data across centers.

All statistical tests will be two-sided and tested at the 5% level of significance.

Analyses will be performed using SAS for Windows statistical software, version 9.4 or higher (SAS, Cary, NC), except where other software may be deemed more appropriate. In the event that other software is used to perform some analyses, the details will be provided in the Clinical Study Report.

■ will perform all efficacy and safety analyses described in this SAP.

Subject data will be listed, sorted by treatment group and subject number. When applicable, listings will be additionally sorted by visit and assessment date/time.

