#### **4.2 Analysis Populations**

The following three analysis populations will be defined for this study:

The intent-to-treat (ITT) population is defined as all subjects who are randomized. All efficacy analyses will be carried out using the ITT population based on the randomized treatment.

The Per-Protocol (PP) population is defined as the subset of subjects included in the ITT population who do not present major protocol violations which might have an impact on the primary efficacy endpoint, and complete at least 80% of the IP. The primary efficacy analyses will be carried out using the PP population if different from the ITT population.

The Safety (SAF) population for the combination arm is defined as the subset of subjects who receive at least any amount of Gamunex-C in addition to SMT. The SAF population for the SMT alone arm will include all subjects randomized to this arm, because by definition SMT is universally provided and hence all randomized subjects would have received SMT. All safety analyses will be carried out using the SAF population based on the treatment actually received rather than randomized treatment.

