### 6.1 Primary Efficacy Endpoint and Analysis

The primary efficacy analysis will be carried out on the ITT population. If there is difference between the PP population and ITT population, the analysis will be repeated using the PP population.

The primary efficacy variable is all-cause mortality rate through Day 29. Subject status (Alive/Death) will be recorded in the database. If the vital status of the subject is missing, then the subject will be treated as death for the primary analysis.

The null hypothesis is that the all-cause mortality rate through Day 29 in subjects administered Gamunex-C plus SMT will be no different than the rate in subjects provided SMT alone;  $H_0: \pi_t - \pi_c = 0$ . The alternative hypothesis is that the all-cause mortality rate through Day 29 in subjects administered Gamunex-C plus SMT will be different than the rate in subjects provided SMT alone;  $H_1: \pi_t - \pi_c \neq 0$ .

The proportion of subjects who die within each treatment group will be presented along with a two-sided exact (Clopper-Pearson) 95% confidence interval (CI).

The observed difference in the mortality rate (proportion of deceased subjects) between treatment groups along with the exact unconditional 95% CI for risk difference will be calculated. The null hypothesis will be tested using Fisher's exact method and the p-value will be reported.

An alternative primary analysis will be performed in which the survival rates will be estimated using the Kaplan-Meier (KM) method. The KM estimates along with 95% CIs and survival curves will be provided. Based on the KM estimates, the survival probabilities and associated 95% CIs on Days 15 and 29 will be reported; in addition, the 25th, 50th (median), and 75th percentiles of the survival time with associated 95% CIs will be provided, as data permit. The survival rates between treatment groups will be compared using Log-rank test and the p-value from Log-rank test will be presented.

Subgroup analyses of the primary efficacy endpoint by baseline characteristics such as age group (with age cutoffs defined either by absolute values or by a summary metric [e.g., median] of the observed baseline values) and gender will be performed using the analysis method described above, if appropriate.

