If for one or more subjects the actual treatment received is different from the randomized treatment and if deemed necessary, sensitivity analysis of the primary efficacy endpoint will be performed by repeating the primary efficacy analysis as described above in this section, but with subjects grouped according to the actual treatment received instead of the randomized treatment.

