### **9. SAMPLE SIZE AND POWER CALCULATIONS**

Because of the urgency and lack of previous prospective COVID-19 data, sample size estimation remains incompletely defined; however the size of this pilot study is commensurate with other Phase 2 investigations ongoing during the COVID-19 pandemic. Approximately 100 subjects are allowed to be randomized as part of a humanitarian effort against COVID-19.

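### The optional as-treated repeat of the Day 29 mortality analysis can favour IVIG, because IVIG subjects who die without an infusion would naturally be counted as SMT alone

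*SAP*

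**What the plan says.** The endpoint is Day 29 mortality ("The primary efficacy endpoint is all-cause mortality rate through Day 29"). SAP 4.2 fixes the grouping: "All efficacy analyses will be carried out using the ITT population based on the randomized treatment". SAP 6.1 then adds a sensitivity analysis that departs from it. If at least one subject's received treatment differs from the assigned one, and the analysis is thought necessary, everything described in that section may be repeated "with subjects grouped according to the actual treatment received instead of the randomized treatment".

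Four other provisions bear on how this would work.

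- SAP 4.2, in defining the safety population, states that SMT is given to all, so every randomised subject has received it.
- SAP 6.1 counts a subject with missing vital status as a death.
- SAP 3.2.3 places the first infusion on Day 1. Protocol 7.2.2 puts randomisation after the baseline assessments and before dosing, and makes the start of infusion subject to a blood-pressure condition.
- Protocol 6.2.2 says: "Administration of other commercial IVIG products during study is not allowed".

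Neither document defines received treatment for this analysis or says where a never-infused IVIG subject belongs.

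**The concern.** A sensitivity analysis of the primary endpoint should show whether the ITT result is robust. Under this regrouping, a subject counts as IVIG only if alive and fit enough to start an infusion. A subject assigned to IVIG who dies first, or deteriorates and is never dosed, has received SMT and nothing else, and so falls into the comparator. Such a death is not merely dropped from IVIG. It is charged to SMT alone, so both rates move in the direction that flatters IVIG.

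Two features add to this. A never-infused subject who withdraws with unknown vital status would also be a death moved to SMT alone, if the missing-data rule carries into the repeat, as the wording implies. And the repeat covers the Kaplan-Meier and log-rank analysis, where time runs from randomisation (SAP 4.6) while IVIG membership depends on reaching the infusion. That is immortal-time bias, even if the interval is short.

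At stake is the value of the check. Agreement with ITT would not be clear reassurance, and a more favourable result could be an artefact. The trial is open-label and no criterion is given for when the repeat is necessary, so the choice to run it could follow sight of the outcomes.

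**Working it through.** **Inputs.** About 100 subjects ("Approximately 100 subjects are allowed to be randomized as part of a humanitarian effort against COVID-19"), allocated equally ("Subjects will be randomized 1:1 to receive either combination treatment with Gamunex-C plus SMT or SMT alone"), so 50 per arm. Tests are two-sided at 5% ("All statistical tests will be two-sided and tested at the 5% level of significance"), and the primary test is Fisher's ("The null hypothesis will be tested using Fisher's exact method and the p-value will be reported"). SAP 9 gives no control mortality, effect size or power, so there is no figure of the plan's own to reproduce. Assumptions: no true effect, and equal mortality of 30% (15/50) in each arm, with a range of 20% to 50%. The number never infused (u) and the number of those who die (m) are not in the documents and are varied.

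**Step 1: only deaths move (u = m = k).** The as-treated comparison becomes (15 - k)/(50 - k) for IVIG against (15 + k)/(50 + k) for SMT alone.

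| k | IVIG | SMT alone | Difference (points) | Fisher p |
|---|---|---|---|---|
| 0 (same as ITT) | 15/50 = 30.0% | 15/50 = 30.0% | 0.0 | 1.00 |
| 1 | 14/49 = 28.6% | 16/51 = 31.4% | -2.8 | 0.83 |
| 2 | 13/48 = 27.1% | 17/52 = 32.7% | -5.6 | 0.66 |
| 3 | 12/47 = 25.5% | 18/53 = 34.0% | -8.4 | 0.39 |
| 5 | 10/45 = 22.2% | 20/55 = 36.4% | -14.1 | 0.19 |
| 8 | 7/42 = 16.7% | 23/58 = 39.7% | -23.0 | 0.016 |

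Over 20% to 50% mortality, one moved death gives -3.2 to -2.0 points and three give -9.6 to -6.0. With otherwise equal arms, p first falls below 0.05 at five moved deaths, and only at 20% mortality (p = 0.049).

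**Step 2: never-infused survivors move too.** The difference is (15 - m)/(50 - u) - (15 + m)/(50 + u). It is negative when (15 - m)(50 + u) < (15 + m)(50 - u), which reduces to 30u < 100m, or m/u > 0.30. So the repeat favours IVIG only when mortality among the never-infused exceeds the arm's own 30%. With u = 4:

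| Deaths among 4 never infused | 0 | 1 | 2 | 3 | 4 |
|---|---|---|---|---|---|
| Difference (points) | +4.8 | +0.8 | -3.2 | -7.2 | -11.3 |

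**Step 3: regrouping against exclusion.** If three uninfused deaths were left out of both arms instead, the comparison would be 12/47 = 25.5% against 15/50 = 30.0%, or -4.5 points. Regrouping gives -8.4, nearly twice that.

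**Step 4: false-positive rate.** This was simulated with no true effect, 50 per arm, 40,000 trials per setting, mortality of 20% to 40%, and only deaths moving. Fisher's test grouped as randomised rejects in 2.8% to 3.3% of trials. The as-treated test rejects as follows.

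| IVIG arm dying uninfused | As-treated rejection rate |
|---|---|
| 2% | 4.3% to 4.9% |
| 4% | 6.4% to 9.6% |
| 6% | 9.8% to 18.2% |
| 10% | 20% to 48% |

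From 4% upwards, almost all of these rejections favour IVIG.

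**The case against.** A reader might infer that this analysis is bound to manufacture a mortality benefit for IVIG, and that movement between groups can go only one way. The documents do not support either.

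First, the reassignment is inferred. SAP 6.1 does not mention uninfused subjects. The nearest rule on treatment received is the safety population in SAP 4.2, which fills the SMT-alone arm with those randomised to it. Read literally, it leaves a never-infused IVIG subject in neither arm. But SAP 6.1 repeats an analysis of all randomised subjects and does not call on the safety population, so counting them as SMT alone remains the natural reading.

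Second, survivors move as well. Protocol 5.3 allows withdrawal before infusion, and Step 2 shows that low mortality among such subjects would bias the repeat against IVIG. This stands: the direction depends on a condition. Excess mortality is plausible, because deterioration is one reason for never starting and unknown status counts as death, but it is not shown.

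Third, the number may be zero. Dosing is planned for Day 1, and Protocol 5.2 excludes irreversible shock with multiorgan failure, refractory hypotension and limits on therapeutic effort. This also stands.

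Fourth, Protocol 6.2.2 bars other IVIG products. It is a rule of conduct, not proof that no SMT subject could receive Gamunex-C. Allocation error or crossover in an open-label trial is an ordinary reason for such a clause.

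Finally, defining the term and reporting how many subjects were regrouped would make the result more transparent. It would not remove the dependence of group membership on surviving to the infusion.

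**Conclusion.** The concern holds as a conditional one. When triggered, the as-treated repeat can bias Day 29 mortality in favour of IVIG, and does so if never-infused IVIG subjects die more often than their arm as a whole. Assuming no true effect, 30% mortality and 50 per arm, one to three moved deaths shift the difference by -2.8 to -8.4 points, without significance when the arms are otherwise equal. The size rests on counts that the documents do not give.

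A reader might also take this as a threat to the main result. It is not. The primary analysis is ITT by randomised arm and is unaffected; the repeat is optional and supplementary. The change is worth making because it is cheap and because, as written, the check is difficult to interpret in just the situation where it would be run.

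**What to change.** In SAP 6.1, remove the regrouping by treatment received. Keep all subjects in their randomised arms, and list never-infused and crossed-over subjects by arm, with the reason and Day 29 status.

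If an effect in treated subjects is wanted, report a complier-average effect: the ITT risk difference divided by (proportion of the IVIG arm starting Gamunex-C minus proportion of the SMT arm starting it), with a bootstrap 95% CI. State the assumption that assignment affects mortality only through infusion. For example, if 47 of 50 IVIG subjects and no SMT subject start, the divisor is 0.94 - 0 = 0.94. An ITT difference of zero then stays at zero, where regrouping three uninfused deaths gives -8.4 points.

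The cost is SAP wording, one listing and, if used, one line of analysis. Much of the listing's content is already collected or reported: SAP 3.2.4 requires reasons for incomplete dosing to be recorded, SAP 5.1 covers disposition, and SAP 6 lists efficacy data. The downside is that the complier-average estimate is slightly less precise than ITT, and close to it when nearly everyone is dosed.

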## 6.2 Secondary Efficacy Endpoints and Analyses

### Time to ICU discharge (Actual and Medical Equivalence)

Time to actual ICU discharge is defined as duration of actual ICU stay from Day 1 through Day 29 that is recorded on the eCRF All Visits page "General Duration of Hospitalization, & Overall Requirement for Mechanical Ventilation, ICU Admission and/or Oxygen Supplementation". The proportion of subjects who are discharged from the ICU will be estimated using the CIF. Deaths that occur prior to discharge from the ICU will be treated as a competing risk. The estimated cumulative incidence and associated two-sided 95% CI on Days 15 and 29 will be displayed. Test for equality of the CIF between treatment groups will be conducted using Gray's test.

Additionally, medical equivalence of ICU discharge date will be recorded on the eCRF if it is different from the actual ICU discharge date, and the time to medical equivalence of ICU discharge will be analyzed using the same method as described above. The proportion of subjects who are medical equivalence of discharge from the ICU will be estimated using the CIF. Deaths that occur prior to medical equivalence of ICU discharge will be treated as a competing risk. The estimated cumulative incidence and associated two-sided 95% CI on Days 15 and 29 will be displayed. Test for equality of the CIF between treatment groups will be conducted using Gray's test.

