### **Time to hospital discharge (Actual and Medical Equivalence)**

Time to actual hospital discharge is defined as duration of hospitalization from Day 1 through Day 29 that is recorded on eCRF All Visits page “General Duration of Hospitalization, & Overall Requirement for Mechanical Ventilation, ICU Admission and/or Oxygen Supplementation”. The proportion of subjects who are discharged from the hospital will be estimated using the CIF. Deaths that occur prior to discharge from the hospital will be treated as a competing risk. The estimated cumulative incidence and associated two-sided 95% CI on Days 15 and 29 will be displayed. Test for equality of the CIF between treatment groups will be conducted using Gray’s test.

Additionally, medical equivalence of hospital discharge date will be recorded on the eCRF if it is

different from the actual hospital discharge date, and the time to medical equivalence of hospital discharge will be analyzed using the same method as described above. The proportion of subjects who are medical equivalence of discharge from the hospital will be estimated using the CIF. Deaths that occur prior to medical equivalence of hospital discharge will be treated as a competing risk. The estimated cumulative incidence and associated two-sided 95% CI on Days 15 and 29 will be displayed. Test for equality of the CIF between treatment groups will be conducted using Gray's test.

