### **Time to clinical response**

Clinical response is defined as the NEWS score <=2 maintained for 24 hours from Day 1 through Day 29. The time to the first occurrence of clinical response will be estimated using the Kaplan-Meier (KM) method. The KM estimates along with 95% CI, and survival curves will be provided. Based on the KM estimates, the probabilities of achieving first clinical response and associated 95% CIs on Days 15 and 29 will be reported; in addition, the 25th, 50th (median), and 75th percentiles of the time to first clinical response with associated 95% CIs will be provided, as data permit. The survival rates between treatment groups will be compared using Log-rank test. The p-value from Log-rank test will be presented.

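### The Gray's and log-rank analyses in SAP 6.2 plan no between-arm estimate with a confidence interval: clinical response has none of its own, and discharge has one only in mean days

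*SAP*

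**What the plan says.** SAP 6.2 analyses time to ICU discharge and time to hospital discharge, each in an actual and a medical-equivalence version. It uses the cumulative incidence function with death as a competing event. For each arm, "The estimated cumulative incidence and associated two-sided 95% CI on Days 15 and 29 will be displayed". The arms are then compared by a test alone: "Test for equality of the CIF between treatment groups will be conducted using Gray's test". No difference in cumulative incidence and no hazard ratio is named.

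Time to clinical response is NEWS of 2 or less held for 24 hours. It gets Kaplan-Meier probabilities at Days 15 and 29 and quartiles, by arm, with 95% CIs. The comparison is a log-rank test: "The p-value from Log-rank test will be presented". Table 1 in SAP 4.4 right-censors deaths for this endpoint.

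The SAP does plan a between-arm estimate with a 95% CI for Day 29 mortality (6.1) and, in 6.2, for the four duration variables (ICU stay, ventilation, hospitalization, oxygen use), the ordinal scale, SOFA and NEWS. For ICU stay and hospitalization this is a difference in least-squares mean days. A subject who dies in the ICU or hospital is counted as staying there to Day 29.

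Protocol 9.1 names only Kaplan-Meier and the log-rank test for time-to-event variables and leaves the detail to the SAP. On size, SAP 9 says that "sample size estimation remains incompletely defined".

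**The concern.** The secondary objective (SAP 2.1.2) is comparative. With no target effect, event rate or power stated, a non-significant result on these endpoints is quite possible. A p-value alone does not separate a small effect from an imprecise estimate. Two arm-level intervals are not an interval for the difference, and judging by whether they overlap is stricter than a 5% test. At stake is whether the report can say how large a benefit or harm on clinical response, or on the proportion discharged by Day 15 or 29, the data are compatible with.

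**Working it through.** **Inputs from the documents.** Level: "All statistical tests will be two-sided and tested at the 5% level of significance". Size: "Approximately 100 subjects are allowed to be randomized as part of a humanitarian effort against COVID-19". Allocation: "Subjects will be randomized 1:1 to receive either combination treatment with Gamunex-C plus SMT or SMT alone". This gives 100/2 = 50 per arm. The SAP states no power, effect or event rate, so there is no figure of its own to reproduce. The incidences and event counts below are assumptions.

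**1. Precision of a difference at one time point.** With the same incidence p in both arms and complete follow-up, half-width = 1.96 × √(2p(1−p)/50).

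| p | Half-width (points) |
|---|---|
| 0.4 | 19.2 |
| 0.5 | 19.6 |
| 0.6 | 19.2 |
| 0.7 | 18.0 |

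For example, 60% against 50% is a difference of 10 points. The half-width is 1.96 × √(0.6×0.4/50 + 0.5×0.5/50) = 19.4, so the 95% CI is about −9 to +29 points.

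**2. Reading the arm-level intervals instead.** At p = 0.5 each arm's half-width is 1.96 × √(0.25/50) = 13.9 points. Two such intervals fail to overlap only if the arms differ by 2 × 13.9 = 27.7 points (before rounding), against 19.6 for significance. The ratio is 2/√2 = 1.41.

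**3. What a log-rank p-value leaves open (clinical response).** With 1:1 allocation and d events in total, log HR ≈ z × 2/√d and its 95% CI is log HR ± 1.96 × 2/√d. For two-sided p = 0.30, z = 1.036.

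| Events (assumed) | HR | 95% CI |
|---|---|---|
| 30 | 1.46 | 0.71 to 2.99 |
| 60 | 1.31 | 0.79 to 2.17 |
| 80 | 1.26 | 0.81 to 1.95 |

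The same p-value fits clearly different estimates and intervals.

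**4. Whether the mean-days difference already supplies the discharge contrast.** With deaths counted to Day 29, full follow-up and a single stay, mean days is essentially the area above the cumulative incidence curve up to Day 29. The planned difference is therefore the area between the two curves, not their gap on a given day. An artificial example shows that the two can diverge:
- Arm A: 50% discharged, all on Day 15, and the rest not discharged. Mean days = 0.5 × 15 + 0.5 × 29 = 22.
- Arm B: 70% discharged, all on Day 19. Mean days = 0.7 × 19 + 0.3 × 29 = 13.3 + 8.7 = 22.

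The difference in mean days is 0, while the difference in cumulative incidence at Day 29 is 20 points.

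**5. Whether the planned Kaplan-Meier estimates can supply a cumulative incidence of response.** They cannot. Censoring deaths treats those subjects as if they could still respond later, so one minus Kaplan-Meier is not the proportion who respond when some die first. The discharge endpoints avoid this and clinical response does not.

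**The case against.** The strongest reply is that the arms are not left without interval estimates on these outcomes, and much of it stands.

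- **ICU and hospital stay.** SAP 2.2.2 defines time to actual discharge as a duration, and version 2.0 of the SAP added duration analyses, actual and medical equivalence, with a difference and 95% CI. A reader might infer that discharge is compared only by a p-value and that the trial can say nothing about effect size there. The documents do not support that. The mean-days difference is a real effect measure, though it does not give the contrast at Days 15 and 29.
- **Neighbouring analyses.** The ordinal-scale odds ratio at Days 15 and 29 has a 95% CI and partly covers hospital status, with death as the worst category. The NEWS mean difference has one on the same days. Neither is an estimate for time to response or for the cumulative incidence of discharge.
- **Survival.** The Kaplan-Meier mortality analysis has the same form: "The survival rates between treatment groups will be compared using Log-rank test and the p-value from Log-rank test will be presented". A reader might count it as a further gap. It is not a material one, because SAP 6.1 already plans the Day 29 mortality difference with an exact unconditional 95% CI.
- **Reconstruction.** The arms are independent, so an approximate difference can be rebuilt from the arm-level intervals, as in step 1. For clinical response, that reconstruction would rest on estimates that censor deaths.
- **Size.** The event rates are assumed, and an interval at one day does not translate a whole-curve test such as Gray's. The ±18 to ±20 points describe what the added interval would look like, not what a non-significant Gray's test excludes.

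**Conclusion.** The point holds as a limited reporting gap. Time to clinical response has a log-rank p-value and no between-arm estimate of its own. Time to ICU and hospital discharge has a between-arm estimate only as a difference in mean days with deaths carried to Day 29, which is a different quantity from the difference in cumulative incidence of discharge with death competing. The planned tests are not wrong, and the gap does not touch the primary analysis.

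At about 50 per arm the missing intervals would be wide, roughly ±18 to ±20 points. That assumes incidences of 40% to 70%, equal in the two arms, and complete follow-up. Reporting them would show the imprecision, not reduce it.

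**What to change.** - **ICU and hospital discharge (SAP 6.2).** Next to Gray's test, add the between-arm difference in cumulative incidence of discharge at Days 15 and 29 with 95% CI, for the actual and medical-equivalence versions. State the variance method.
- **Clinical response (SAP 6.2 and Table 1).** Estimate the cumulative incidence of response with death as a competing event, as for discharge, and report the between-arm difference at Days 15 and 29 with 95% CI. If Kaplan-Meier is kept, label the contrast as a difference in Kaplan-Meier probability with deaths censored. The log-rank p-value may stay.
- **Survival (SAP 6.1).** No change is needed.

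This adds ten differences: four discharge analyses plus clinical response, at two days each. The cost is a few lines of SAP text, a little programming and slightly longer tables. An interval at one day and a whole-curve test can disagree, so the SAP should say that the intervals are descriptive and, in line with SAP 4.5, not adjusted for multiplicity.
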